6.3 Ethical Review and Regulatory Consideration

The study will be conducted according to the Declaration of Helsinki 2013 (30), this Clinical Investigational Plan (CIP), national and local laws, regulations, standards, and requirements of the countries where the study is being conducted, including data protection laws.

In addition, to follow the governing regulations noted above, any additional requirements of the individual study center's EC/IRB or regulatory authority will also be followed by the study center where applicable.

All required regulatory notifications / approvals for non-interventional studies will be followed according to each country.

The GOLD AF Registry was designed to reflect the GCP principles, including the protection of the rights, safety and well-being of human subjects, controls to ensure the scientific conduct and credibility of the clinical investigation and the definition of responsibilities of the sponsor and investigators.

The international ethical and scientific quality standards and principles of the Declaration of Helsinki 2013 (30) and later versions throughout the study and the good clinical practice (GCP) (31) are implemented in this study by means of the Patient Informed Consent (PIC) process, EC/IRB approval, study training, clinical trial registration, risk benefit assessment, publication policy, etc. The study will be conducted according to national and local laws, regulations, standards, and requirements of the countries / geographies where the study is being conducted and the Clinical Investigation Plan (CIP), Clinical Trial Agreement (CTA) at each participating site.

This study will be publicly registered (see chapter 9).

GOLD AF registry will be submitted to EC/IRB/CA for approval/notice if required by local law. In addition, Regulatory authorities will be notified and approval sought as required by local laws and regulations. Progress reports will be submitted to ECs/IRBs and regulatory authorities as required by local laws and regulations.

The Sponsor will avoid improper influence on or inducement of the patients, monitor, any PI(s) or other parties participating in, or contributing to, the study. All PIs shall avoid improper influence on or inducement of the patients, sponsor, monitor, other PIs or other parties participating in or contributing to the study.

6.4 Amendments to the CIP

Medtronic and/or designee (CRO) will submit any amendment to the CIP, including a justification for this amendment, to the appropriate regulatory authorities and to the PIs to obtain approval from their EC/IRB, if applicable. Furthermore, Medtronic and CRO study management and shall provide review and approval of each amendment, as applicable according to the function in the study.

6.5 Data Protection

All records and other information concerning patients participating in this study will be treated as confidential. Patients' data will be stored and processed in pseudonymized form, i.e. without referencing patients' name or initials. An identification number assigned to each patient will be used in lieu of the patient's name to protect the patient's identity when analyzing and reporting registry-related data. Study data may be transferred to the United States of America and other countries' entities for processing. However, the patients' privacy will be maintained according to the requirements of Data Protection Directive 95/46/EC and national legislation for data protection.

Authorized personnel (hospital and specialized site staff, representatives of the Sponsor and CRO) will have access to personalized patient data in original source documents (medical records). Patient will agree to this by signing patient informed consent or data release form.

6.6 Insurance and Liability

The liability of the participating physician is the same as their standard medical practice as this is an observational study. As this is an observational study, patient's insurance **statement/certificate** will only be provided if required by the local law.

7 Warranty information will be provided in the product packaging. CE certificated copies are available upon request. Recording Keeping, Data Reporting, and Data Quality Assurance

Data quality assurance will include handling rules for missing or incomplete data, and range checks (i.e., age, date, etc.), along with data transformations. Data quality checks will be described in the Data Management Plan.

The PI will comply with the confidentiality policy as described in the CTA. He/she will comply with the CIP (which has been notified or approved (if applicable)) by the respective EC/IRB and the requirements described in the CTA between Medtronic and the site. The PI is ultimately responsible for the conduct of all aspects of the registry at the participating site and verifies by dated signature the integrity of all data transmitted to the sponsor.

7.1 Data Collection Procedure

Data will be collected via electronic case report forms (eCRFs) via a web-based study database using the software solution EBogen©, developed by the IHF GmbH, Ludwigshafen, Germany.

The GOLD AF database is reachable over the following link: <http://studien.herzinfarktforschung.de/goldaf>.

Case report forms for this study will be provided under separate cover. Final eCRFs will be provided to sites via the electronic data system after the site has fulfilled all requirements for database access.

Data will be stored in a secure, password-protected database which will be backed up hourly. Data will be reviewed using programmed and manual data checks. Data queries will be made available to study sites for resolution. Study management reports may be generated by the sponsor (and/or CRO) to monitor data quality and study progress. The investigator is responsible for the oversight (review and signature) of the eCRFs.

At the end of the study, the data will be frozen and retained and will be retained per sponsor policy.

Prerequisites for using the EBogen© system include, internet access using a current web browser (Internet Explorer 8 or later, Firefox, Chrome or Safari) supporting JavaScript. No local software installation is required.

7.1.1 Data collection

The PI must ensure accuracy, completeness and timeliness of the data reported in the eCRFs and in all other required reports. Data reported on the eCRFs which are derived from source documents must be consistent with the source documents or the discrepancies need to be justified by a documented rationale, signed and dated by the site investigator, to be entered in the EBogen© system. Only authorized persons can complete eCRFs. eCRFs shall be signed by PIs as specified on the Delegated Tasks List included in the Investigator Site File (ISF). All efforts should be made to complete 100% of data collection of required variables.

7.1.2 Data review and processing

All collected data will be reviewed for completeness, correctness and consistency. In case of issues, queries will be sent to the respective PI to complete, correct or comment the data.

In order to document that the site has completed data entry for an EBogen section, they have to be signed by the authorized personal.

If any changes are needed in the CRF, signature can be revoked by investigators and /or authorized personal with specifying the reason of signature revoke (e.g. need to add data, need to correct data etc.). After changes in the CRF it should be signed again as a completed one.

All efforts should be applied by the participating site staff to answer 100% of site queries.

7.2 Data collection process

All follow up (FU) visits in this registry will be performed in accordance with standard of care in participating medical centers.

Data from "routine" FUs should be reported in "General FU" case report form (CRF). If a patient visits the medical center within the period 12-14 months after the index Phased RFA, this data should be documented in the "12 months in hospital FU" CRF, which contains the QoL questionnaire, additionally to the "General FU" information. If "12 months in hospital FU" was completed in the database, no further FU visits are required, and the patient exits the study. "Exit form FU" CRF is not required.

If after 12 (+1) months from the procedure the "12 months in hospital FU" CRF was not completed in the database, study personnel will receive a notification to conduct 12 months FU by phone and fill in "12 months phone FU" CRF. Therefore "12 months in hospital FU" CRF can be completed within 12 - 14 months after the index Phased RFA. Between 13 and 14 months after the index Phased RFA either "12 months in hospital FU" or "12 months phone FU" CRFs (whatever occurs first) can be completed (Figure 7-1).

[figure not shown]

Figure 7-1: 12 months FU management.

Enrollment

A patient is eligible if he/she meets the eligibility criteria described above. Enrollment of a patients is complete once consent (PIC/PDRF and/or authorization/privacy form) has been obtained.

Patients can be enrolled starting from 14 days prior to the hospitalization for the index Phased RFA procedure, as well as during the hospital stay.

Baseline

The baseline visit can occur the same day as enrollment, however, consent should be obtained prior to any data collection.

The "Baseline" CRF will be used to collect demographic data, primary indication for Phased RFA, cardiovascular diseases history, arrhythmia status, history of AF, symptoms, concomitant diseases, diagnostics, cardiovascular medication. QoL questionnaire "AFEQT" will be completed by the patient and data transferred to eCRF.

Procedure visit

The procedure will be performed according to the hospital's standard Phased RFA practice.

The "Procedure" CRF will be used to collect data about the ablation procedure and discharge from the medical center. Information regarding anticoagulation therapy, procedure summary information, sedation and consumables, PVI confirmation, cardiovascular medication, date and status at hospital discharge is to be collected. Verification of study defined AEs will be done during the procedure and at the moment of hospital discharge.

If the attempt to conduct Phased RFA ("index" procedure) is not successful for clinical or technical reason, patients will stay enrolled into the registry. If Phased RFA is repeated ("repeated" procedure) or re-do due

to arrhythmia recurrence, the “procedure” CRF should be filled in. Information about all Phased RFA attempts will be used for the analysis. If patient has re-do procedures with some other technology than Phased RFA, Procedure CRF is not required; information about technology which was used for re-ablation to be collected in eCRF “General FU”.

During the Phased RFA, the investigator may require use of other commercially available devices for other ablations such as Afi/LAT or other AF triggers. The use of other devices will be at the investigator’s discretion and use will be documented on the eCRF.

Hospital discharge needs to be completed when the patient is discharged from the hospital, this data to be collected as a part of the procedure visit. Information about date of discharge, reportable adverse event since the procedure and recommended medication information is to be collected. Post-ablation drug regimen is determined at clinical discretion of the treating investigator.

General Follow up visits (in hospital)

The “General” FU CRF will be used to collect data during all standard visits at the site within the following 12 months after the index or study procedure. Data to be collected include: arrhythmia assessment, diagnostics, symptoms, hospitalizations, ablation information and medication. If “General FU” will take place due to system/procedure related AE, “Adverse Event” CRF should be filled in additionally to the “General” FU CRF.

If at any moment during FU, the patient withdraws PIC/PDRF or PI receives information about the patient’s death, the “Exit” CRF should be filled in addition to the “General FU” CRF. All data collected prior to the patient exit will be used for analysis, unless different is required by local laws and regulations.

12 months FU (in hospital or by phone)

If the patient appears in the participating medical center within 12 - 14 months after the index procedure, the “in hospital 12 months FU” CRF should be completed. If an “in hospital” visit does not occur after 13 months post index procedure, the site should apply all efforts to conduct interview by phone and document it in “12 months phone FU” CRF. The phone FU interview does not replace a medical checkup for the patient and serves as data collection, only.

Data to be collected during 12 months FU includes arrhythmia assessment, diagnostics, symptoms, hospitalization and re-ablations occurred since last visit, medications, QoL questionnaire.

To ensure a unified approach and to minimize possible bias, all sites will be trained to use the standardized “patient questionnaire for phone FU” with questions regarding parameters of interest equivalent to eCRF variables. In Germany, the phone FUs can be performed by Institut für Herzinfarktforschung, GmbH.

If study personnel obtain information during the phone FU that patient will appear in the hospital before the end of FU window, it is under site consideration to complete „12 months phone FU” CRF or conduct a medical check -up and complete „in hospital 12 months FU”.

Study Exit

Prior to exiting a patient from the study, it is recommended to follow the patient until all ongoing reportable AEs are resolved or unresolved with no further actions planned. Upon exiting from the study, no further study data will be collected or study visits will occur for the patients. All data available through the time of the subject’s exit will be used for analysis.

Patients are urged to remain in the study until the end of individual follow up but may be exited from the study for any of the following situations:

- Patient lost to follow up
- Patient chooses to withdraw (e.g., consent withdrawal, relocation to another geographic location)
- Investigator deems withdrawal necessary (e.g., medically justified, , failure of subject to maintain adequate study compliance)
- If patient were enrolled with the intention to perform Phased RFA, but get ablation with another technology
- Death

If patient has enrolled into study and vascular access was obtained with the intention of completing the study Phased RFA, but the subject did not receive any ablation energy, or complete entire study

procedure, sites will be asked to keep patients enrolled for 30 days to ensure potential procedure / device related AEs are assessed and collected. If there are no related.

All subject deaths must be reported by the investigator to Medtronic on an Exit Form as soon as possible after the investigator first learns of the death.

In the event of a patient's death, the investigator is responsible to assess at their own discretion whether or not the death is related to the procedure and/or the system.

If any relatedness is assessed, it is required also the completion and reporting of a Serious Adverse Event (SAE) form (see paragraph 11.1.1). Data collection requirements are summarized in Table 7-1 below.

Table 7-1: Data collection requirements at subject visits

| Data Collection* | Baseline | Procedure | General FU | 12 Months FU | 12 Months FU by phone |
|--------------------------------------|--------------------|------------------|-------------------|---------------------|------------------------------|
| Enrollment (PIC/PDRF) | X | | | | |
| Demographics | X | | | | |
| Medical History [#] | X | | | | |
| Concomitant disease | X | | | | |
| Diagnostics | X | | X | X | X |
| Symptoms | | | X | X | X |
| Medication list | X | | X | X | X |
| Administrative information | | X | X | X | X |
| Anticoagulation pre-intra-procedural | | X | | | |
| General procedure summary | | X | | | |
| Consumables | | X | | | |
| PVI confirmation | | X | | | |
| Hospital discharge | | X | | | |
| Quality of Life (AFEQT) | X | | | X | X |
| History of AF since last visit | | | X | X | X |
| Hospitalization | | | X | X | X |
| Reportable Adverse events** (AEs) | - Whenever occur - | | | | |
| Study Exit | - Whenever occur - | | | | |
| Study Deviation form *** | - Whenever occur - | | | | |

* prior to first patient enrollment every site needs to fill in a site questionnaire once #= Medical history includes questions about prior CVD, history of AF, main underlying disease, concomitant disease and history of AF.

** Data collecting requirement for Adverse Event eCRF described in chapter 11 "Adverse Event"

*** Data collecting requirement for Deviation eCRF described in chapter 7.4 "Study Deviations"

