3.2 Study Population/Selection Criteria

Patients with paroxysmal, persistent and long-standing persistent AF who fulfill inclusion criteria.

Inclusion criteria:

- Patient with AF who is scheduled for Phased RFA procedure
- Patient signed Patient Informed Consent (PIC) or Patient Data Release Form (PDRF)
- Age ≥ 18 years old

Minimization of Bias

Selection of sites, selection of subjects, and evaluation of study data are potential sources of bias. Methods incorporated in the study design to minimize potential bias include (but are not limited to):

- No exclusion criteria will be defined to reflect “real world” clinical practice approach to the Phased RFA therapy.
- Data collection requirements and study procedures will be standardized across all study centers.
- All study clinicians, participating site personnel, Medtronic and IHF (heater “CRO” can be used) personnel will be trained on the respective aspects of the study using standardized training materials.

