3.4 Methodology

Patient can sign PIC/PDRF 14 days prior to the scheduled Phased RFA procedure to have sufficient time to consider the participation in the registry.

Observations will be documented at baseline, ablation procedure/hospital discharge and whenever patients visit the medical center with regard to AF recurrence, catheter ablations, Adverse Events, regular medical checkup etc.

Patient will be followed up for minimum 12 and maximum 14 months following first (hereafter "index") Phased RFA procedure. In case the index procedure is performed, but is not successful for medical or technical reasons, patients will stay in the registry until the end of the FU period.

Figure 3-5 provides an overview of the data entry flow chart. The process of data collection is described in Chapter 7. Furthermore, an overview of data to be collected is provided in Table 7-1.

At the baseline visit demographics, medical history, diagnostics, cardiovascular medication and quality of life (QoL) questionnaire ("AFEQT") will be recorded. During the index Phased RFA and all re-do Phased RFA procedures, related variables will be collected including: anticoagulation therapy, general procedure summary, consumables, PV isolation confirmation, adverse events (AE) assessment and hospital discharge status. During the FU period, information about in-hospital visits will be captured in the "General FU" CRFs. The "General FU" CRF contains data about arrhythmia diagnostics, symptoms, hospitalization and cardioversions (from previous visit date to actual visit), re -ablation information, cardiovascular medication, and AE assessment.

At 12 months FU, patients will be either followed up in the medical center ("12 months FU") or by phone ("12 months FU by phone"). Data recorded on the "12 month follow up" CRF is equivalent to the "General FU" CRF, with the addition of the QoL questionnaire (AFEQT). If patient has no reason to visit the medical center between 12 and 13 month after the index procedure, he might be called by study personnel and asked questions for about 15-20 min about any AF symptoms, hospitalizations, AF cardioversions since the previous visit, current medications and quality of life. Whenever 12 months FU performed by phone, data received via CareLink may be used for confirmation of rhythm disturbances. The interview does not replace a medical checkup for the patient and serves as data collection only.

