It is recommended that the questionnaire be completed at baseline and at 12 months FU. At baseline AFEQT can be completed starting from 14 days prior to the hospitalization for the index Phased RFA procedure if patient consent his/her participation in the registry.

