## 3 Study Design

### 3.1 Design

The GOLD RF registry is a postmarket release (PMR), prospective, observational, multi-centre, clinical study in consecutive subjects with atrial fibrillation treated with the phased RFA technology (Medtronic, Minneapolis, MN, USA). Patient's participation in this study has no impact on his or her indication, diagnostics or therapy. Subjects are supposed to be treated in compliance with current valid Instructions for Use (IFU) as well as according to medical society guidelines and the clinic's internal directives. Medication-based therapy should also meet medical society guidelines or the clinic's internal directives, respectively.

[figure not shown]
40 sites in 14 countries (Germany, Netherlands, United Kingdom, Hungary, Italy, Spain, Switzerland, Israel, Poland, Portugal, France, Greece, Georgia and South Korea) are anticipated to take part in the registry to get documentation on at least 800-1000 patients (for more details regarding sample size consideration, see Section 3.3 in the SAP). Eligible for participation are study sites and hospital-based physicians treating AF subjects with phased RFA technology. The enrolment period is estimated to be 24 months. The individual observation period per patient is up to 12 (+2) months: Based on the observational plan, it is planned that the baseline visit is conducted by the investigators. All follow-up visits in the registry are unscheduled. They will be conducted in accordance with "routine clinical practice" in the participating medical centres: Between the procedure date and the following 12MFU period, any general FU will be captured. General FUs might occur due to site specific visit schedule, related to AF re-occurrence (re-ablation, AF symptoms, CV etc.) or due to patient visits at the site because of AE related symptoms. At 12MFU window, the patient will either be followed up in the medical centre or by phone.

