### 4.2 Baseline Analysis Set

The *Baseline Analysis Set* (BAS) consists of all patients of the APS and patients:

- where baseline signature has been taken (signed eCRF)
- with AF who are scheduled for Phased RFA
- that meet all remaining eligibility criteria
- provide any further documentation at baseline
- a phased RFA procedure was started - procedure form was fulfilled at least: date of the procedure, PVAC GOLD catheter used (opened), number of PV applications > 0
- patient did not exit the study prematurely for the reason: Patient were enrolled, but Phased RFA procedure was not started

According to the Appendix B, the BAS will be used for the interim and final analysis as well as for post-hoc analysis. The final analysis includes the additional objective (SAP chapter 8.2) and ancillary objectives (SAP chapter 8.3), where the BAS will be applied.

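### Protocol 7.2 does not require consent before the index ablation: enrolment after acute outcomes are known is not excluded, no SAP analysis set checks for it, and *consecutive* in SAP 3.1 has no support

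*Protocol*

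**What the plan says.** **Enrolment window.** Protocol 7.2 (Enrollment) lets patients be enrolled from 14 days before the hospitalization "for the index Phased RFA procedure, as well as during the hospital stay". The window has an opening date, but the start of the ablation is not given as its end. On the baseline visit the same section says that "consent should be obtained prior to any data collection".

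**Text pointing to earlier enrolment.** The first inclusion criterion in Protocol 3.2 is "Patient with AF who is scheduled for Phased RFA procedure". Protocol 3.4 says "Patient can sign PIC/PDRF 14 days prior to the scheduled Phased RFA procedure". The Study Exit rules in Protocol 7.2 cover patients enrolled for Phased RFA who are then ablated with another technology, and patients already enrolled when vascular access is obtained. Table 7-1 puts enrolment and the first AFEQT in the Baseline column, ahead of Procedure.

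**Baseline AFEQT.** Protocol 3.5: "At baseline AFEQT can be completed starting from 14 days prior to the hospitalization for the index Phased RFA procedure". This too has a start but no stated end.

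**SAP.** Section 3.1 describes a "clinical study in consecutive subjects with atrial fibrillation treated with the phased RFA technology". Section 4.1 requires signed consent with a complete date. Section 4.2 requires, among other things, patients "with AF who are scheduled for Phased RFA", the remaining eligibility criteria, a procedure date and at least one PV application. Neither section compares the two dates.

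**The concern.** Acute procedural success is known when the procedure ends. Part of the 30-day safety result (SAP 8.2.1) and of the TIA/stroke result over the first three days (Protocol 4.4.3) is known before discharge. If a site may ask for consent after that, the decision to enrol can depend on the outcome being estimated.

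Protocol 6.1 requires the patient to sign and date the form personally, so a patient who dies or cannot consent after a complication could not be enrolled late at all. A registry meant to describe real-world practice would then report acute results from a selected group, and nothing in the planned output would show it. A first AFEQT completed after ablation would not be a baseline for the change score in SAP 8.3.5.

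Protocol 3.2 names subject selection as a possible source of bias, but none of the measures it lists concerns consent timing or completeness of inclusion.

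**Working it through.** The plan gives no figure on this point, so there is none to reproduce. The check is a reading of the text, followed by an illustration of size.

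**Step 1. Does any other provision close the window?**

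- *Scheduled* (Protocol 3.2, SAP 4.2): implies that the procedure lies ahead, but sets no order between consent date and procedure date.
- Protocol 3.4: says when a patient *can* sign; it is permissive.
- Exit and vascular-access rules (Protocol 7.2): describe patients who were enrolled first; they do not forbid later enrolment of others.
- Consent before data collection (Protocol 7.2): procedure data can be entered from the record after a later consent, so this condition can be met without consent before the ablation.
- Deviation list (Protocol 7.4): refers to consent before participation, not before the procedure.
- SAP 4.1 and 4.2: use a consent date and a procedure date, but never compare them.

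The window is therefore ambiguous, and no check would reveal late enrolment.

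**Step 2. Is *consecutive* supported?** Protocol 3.1 describes the cohort without that word. The Protocol contains no rule for consecutive inclusion and no log of Phased RFA patients who were not enrolled. The archive list in Protocol 16 has only a Subject Identification Log.

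**Step 3. How large could the effect be?** Let *p* be the true event rate, *s* the share of patients approached only after ablation, and *r* the chance that a patient with the event is enrolled late, relative to one without it.

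Observed rate = *p*[(1−*s*) + *s·r*] / [(1−*s*) + *s*(*p·r* + 1 − *p*)]

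Take *p* = 3.9%, the survey complication rate cited in Protocol 4.4.2, as a stand-in for the true rate. The documents give neither *s* nor *r*; both are assumed.

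With *s* = 0.5:
- *r* = 0: 0.0195 / 0.9805 = 1.99%
- *r* = 0.5: 0.02925 / 0.99025 = 2.95%
- *r* = 2: 0.0585 / 1.0195 = 5.74%

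| *s* | *r* = 0 | *r* = 0.5 | *r* = 1 | *r* = 2 |
|---|---|---|---|---|
| 10% | 3.52% | 3.71% | 3.90% | 4.27% |
| 25% | 2.95% | 3.43% | 3.90% | 4.83% |
| 50% | 1.99% | 2.95% | 3.90% | 5.74% |

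In the extreme case *s* = 100%, *r* = 0.5 gives 1.99% and *r* = 2 gives 7.51%.

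Other endpoints at *s* = 50%, *r* = 0.5:
- stroke/TIA, 1.1% (Protocol 4.4.2): 0.83%
- acute failure in paroxysmal AF, 100 − 98.2 = 1.8% (Protocol 4.4.3): 1.36%
- acute failure in persistent AF, 100 − 96.3 = 3.7% (Protocol 4.4.3): 2.80%

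**Step 4. Compare with sampling error.** At n = 1000 the 95% half-width is 1.96·√(0.039 × 0.961 / 1000) = 1.2 points, or 1.3 with the plan's design effect of 1.2. The shift at *s* = 50%, *r* = 0.5 is 3.90 − 2.95 = 0.95 points, inside that. At *r* = 0 it is 3.90 − 1.99 = 1.91 points and at *r* = 2 it is 5.74 − 3.90 = 1.84 points, both outside it. Unlike sampling error, selection does not shrink as n grows.

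**The case against.** The strongest reply is that the Protocol, read as a whole, means enrolment before the procedure. A patient already ablated is no longer scheduled; eligibility is part of SAP 4.2; the exit rules and Table 7-1 assume enrolment first; and consent during the hospital stay most naturally means on admission. Protocol 7.2 also has adverse events verified during the procedure, which, with consent ahead of data collection, again suggests consent first. This stands as evidence of intent. It does not supply a rule or a check.

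Four stronger readings are tempting, and the documents do not support them.

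- *The Protocol permits enrolment at any point in the stay, including after ablation.* It does not say so. The phrase is open-ended and other text points the other way.
- *The safety and acute-success results will look too good.* The direction depends on *r*. If sites enrol complicated cases more readily, the complication rate is overstated. Events that appear after discharge cannot influence in-hospital enrolment, so applying selection to the whole 3.9% exaggerates the shift for a given *s* and *r*.
- *Accrual per site shows that enrolment was not consecutive.* Without the number of eligible patients it shows nothing. The site questionnaire covers the three years before enrolment (Protocol 3.6.1), so it cannot serve as a capture denominator.
- *Late-consented patients should leave the main analysis.* That would conflict with Protocol 4.1, which includes all enrolled patients.

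**Conclusion.** The point holds as a gap in the plan, not as demonstrated bias. Consent before the index ablation is implied in several places and required in none. The SAP would not detect late consent, and *consecutive* rests on no enrolment rule.

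The number of patients affected is unknown and may be zero. With a true complication rate of 3.9% and half of patients approached only after ablation, the observed rate lies between about 2.0% and 5.7% as *r* goes from 0 to 2. With 10% approached late, the same range of *r* gives 3.5% to 4.3%. These figures show what the open window could do under assumed inputs; they are not estimates for this registry.

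The endpoints concerned are acute success, peri-procedural and 30-day safety, TIA/stroke and the AFEQT change score. The point is not made against the 12-month success rate.

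**What to change.** 1. **Protocol 7.2.** After the words on the hospital stay, add *before the start of the index procedure*. On the tentative schedule recruitment ended in Q2 2018, before SAP version 1.1 of December 2018. If enrolment has closed, items 2 to 4 carry the remedy.
2. **SAP, analysis sets and sections 8.2 and 8.3.** Compare the PIC/PDRF date with the index procedure date; both are already collected. Tabulate patients consented before, on the same day as, and after the procedure. Repeat acute success, peri-procedural and 30-day safety, and TIA/stroke in patients consented before the procedure day. The documents show a consent date but no consent time, so flag same-day consents and include them in a second version. Keep all enrolled patients in the main analysis, as Protocol 4.1 requires.
3. **SAP 8.3.5.** Use an AFEQT as baseline for the change score only if it was completed before the procedure, and flag same-day or later ones. Confirm that a completion date is available; Protocol 3.5 mentions dating only where site staff sign for the patient.
4. **SAP 3.1.** Delete *consecutive*.

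The cost is a one-clause clarification, a small extra table and a sensitivity analysis with slightly fewer patients. If the table shows that nobody consented on or after the procedure day, the concern about acute success and safety is closed.
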